Primary outcome: death or MAC – a binary, composite variable defined as the development of an organ/space SSI, enteric suture line failure (aka anastomotic leak), fascial dehiscence, or an unplanned return to the OR for an abdominal complication – within 30 days.

Secondary outcomes:

- Non abdominal morbidities – acute kidney failure, adult respiratory distress syndrome, deep vein thrombosis (DVT), pulmonary embolism, pneumonia, and

urinary tract infection, all identified based on standardized definitions used in the National Trauma Databank, to which MHH-TMC already provides patient data.

- Hospital-, ICU-, ventilator-free days – defined as: 30 – total hospital days/ICU days/ventilator days alive = hospital-, ICU-, and ventilator-free days.
- Hospital costs – to be obtained from MHH-TMC
- Patient-centered outcomes – Standard Gamble, EuroQOL-5D(5L), and the Post-Traumatic Stress Disorder Check List-Civilian (PCL-C) to be administered at discharge and 6 months after discharge.

Study Design

This is a single center, RCT involving patients requiring an emergent trauma laparotomy within the first 90 minutes following ED admission due to a severe abdominal injury.

Intervention

Control – DCL

[figure not shown]
Intervention – DEF

Setting

This study will be conducted at the Texas Trauma Institute at Memorial Hermann Hospital-Texas Medical Center (MHH-TMC). It is one of two Level 1 trauma centers in the Houston metropolitan area, an area in which over 6 million people reside, and is the busiest trauma center in the country, with over 6,000 trauma admissions per year. Approximately 220 emergent trauma laparotomies are performed each year, of which 25-35% are DCLs.

Time Period

IRB submission will occur in January 2016, with community consultation beginning shortly thereafter. Eligible patients will be enrolled starting on July 7, 2016. Enrolled subjects will be followed during their post-laparotomy hospitalization and for 6 months following their hospital discharge to assess patient-centered outcomes.

Outcomes

The primary outcome for this study will be a composite variable composed of the following death or major abdominal complications (MAC) within 30 days:

- Deep or organ/space SSI, as defined by the Centers for Disease Control and Prevention¹⁴

- Enteric suture line failure (enteric anastomotic leak) – leakage of enteric contents from gastrointestinal anastomosis

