- Fascial dehiscence or evisceration – separation of closed fascia with or without protrusion of intestines (to be determined by independent, blinded surgeon)
- Unplanned return to OR after fascial closure for intra-abdominal complication
We hypothesize that patients randomized to DCL will have a higher rate of the primary outcome than those randomized to DEF.

Secondary outcomes will include non-abdominal morbidities, in-hospital mortality or discharge to hospice (as patient is being discharged in order to die with comfort, this will be considered the same as an in-hospital mortality), hospital-/ICU-/ventilator-free days, total hospital stay costs as provided by Memorial Hermann, and patient-centered outcomes.

Non-abdominal complications will be identified based on standardized definitions used in the National Trauma Databank and include: acute kidney failure, adult respiratory distress syndrome (ARDS), deep venous thrombosis (DVT), pulmonary embolism, pneumonia, and urinary tract infection.

Per-patient cost information will be obtained from the hospital and used to study the healthcare resource utilization of DCL.

For patient-centered outcomes, the patients' health state will be queried at discharge and 6 months after discharge using the Standard Gamble and EuroQol-5D(5L).^{15,16} The Posttraumatic Stress Disorder Check List-Civilian [PCL-C] will also be administered 6 months after discharge. Additionally, time to return to work will also be obtained at the 6 month interview.

Overall safety data (compared to historical controls) will be assessed every 6 months throughout the study period by a data safety and management board (DSMB), which will be organized by CeTIR and headed by [name]. The DSMB will also include an anesthesiologist, another independent surgeon, a former trauma patient without a medical background who underwent emergent laparotomy, and an independent statistician.

Study Population

Screening

Clinical research staff will be available on a 24/7 basis to conduct screening and collect data on those patients meeting inclusion criteria. Direct patient observation and data collection will begin immediately upon the patient's arrival to the ED and will continue until 1) it is determined that patient does not meet all inclusion criteria, 2) the surgical procedure has been completed, or 3) the patient dies.

Inclusion/Exclusion Criteria

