Allocation will occur through sequentially numbered, opaque envelopes kept in the research assistants' office and opened in the operating room. An independent statistician will determine the randomization sequence and oversee the labeling of cards and envelopes. A 1:1 allocation ratio using a permuted block design of 4 or 6 will be used to ensure equal number of patients in each group.

Randomization will occur during the emergent trauma laparotomy. The research assistant will query the attending trauma surgeon periodically throughout the procedure to determine their

Figure 3: Trial randomization flowchart

equipoise between DCL and DEF. If the patient meets all eligibility criteria, that patient will be randomized to DCL (control) or DEF (intervention). The research staff will open the opaque envelope to notify the attending surgeon which group to which the subject has been randomized.

Data Collection

All data will be collected by research assistants utilizing a standardized case report form and entered into a RedCap™ database. Each subject will be assigned a study-specific number. Data will be collected from the clinical pre-hospital emergency medical services run sheets, in hospital records, and the trauma registry. Data will be collected until hospital discharge and questionnaires at discharge and 6 months later.

Data collected will include: demographics, prehospital and injury information, hospital information including ED, OR and post-operative care, discharge information, follow up clinic visits, healthcare cost assessments, and the health status questionnaires completed at discharge and 6 months following injury.

Only laboratory values ordered for and used in standard clinical practice will be collected. No study-specific laboratory tests will be ordered. No biologic specimens will be kept or used.

Follow up

No study-specific follow-up will be required. Six-month questionnaires will be performed by phone call. \$5 Starbucks gift cards will be provided to patients who complete the 6 month follow up questionnaires.

Data and Safety Monitoring

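### The six-month patient-centred assessment is timed from discharge almost everywhere but from injury in one phrase, and the dominant discharge rule ties the Aim 3 time point to length of stay

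*Combined protocol and SAP*

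**What the plan says.** Most of the protocol counts the six months from discharge.

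- Objectives, Secondary outcomes: the Standard Gamble, EQ-5D-5L and PCL-C are "to be administered at discharge and 6 months after discharge".
- Study Design, Time Period: subjects are followed "for 6 months following their hospital discharge to assess patient-centered outcomes".
- Study Design, Outcomes: "the patients' health state will be queried at discharge and 6 months after discharge" (Standard Gamble and EQ-5D-5L), and the PCL-C "will also be administered 6 months after discharge".

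Three other places imply the same origin. The title page gives subject duration as the hospital stay plus six months. The first paragraph of Data Collection and the Data Handling section both state: "Data will be collected until hospital discharge and questionnaires at discharge and 6 months later".

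One phrase differs. The second paragraph of Data Collection lists "the health status questionnaires completed at discharge and 6 months following injury".

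Return to work appears under Outcomes: "time to return to work will also be obtained at the 6 month interview". No start date is given for that time. No section gives a call window or says which origin prevails.

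**The concern.** Two separate matters arise.

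The first is a contradiction in current text. Data Collection disagrees with the outcome definitions and with its own preceding paragraph, and it is a section that staff would naturally consult when scheduling calls.

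The second is what the dominant rule does to the comparison. Randomization takes place during the index laparotomy, so discharge is a post-randomization event. Lengths of stay are compared under Aim 1, and hospital-free days are a secondary outcome. If stay differs between arms, a call fixed at six months after discharge reaches the two arms at different times since injury. Health status, post-traumatic stress symptoms and return to work can all change over that period. The at-discharge questionnaire has the same feature.

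Aim 3, with its own planned publication, rests on these measures. Aim 4 uses the trial to estimate effect sizes for a multicenter study, so an unclear time point could carry into the next design.

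**Working it through.** The plan states no figure on this point, so there is none to reproduce. The check is a comparison of the text followed by an illustration.

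**1. Time origin by section**

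| Place | Origin |
|---|---|
| Title page, subject duration | discharge (implied) |
| Objectives, Secondary outcomes | discharge |
| Study Design, Time Period | discharge |
| Study Design, Outcomes: Standard Gamble, EQ-5D-5L | discharge |
| Study Design, Outcomes: PCL-C | discharge |
| Study Design, Outcomes: return to work | none stated |
| Data Collection, first paragraph | discharge (implied) |
| Data Collection, second paragraph | injury |
| Data Handling | discharge (implied) |

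Discharge is the rule, and injury is the single exception.

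**2. Effect of discharge timing on time since injury**

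Take six months as 182.6 days. Then

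days since injury at the call = 182.6 + length of stay.

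For assumed stays of 7, 14, 30 and 60 days the call falls at about day 190, 197, 213 and 243. Timed from injury, it falls at day 183 for everyone. The 182.6 cancels between arms, so the gap in mean time since injury equals the gap in mean stay. Assumed gaps of 7, 14 and 21 days are 7/182.6 = 3.8%, 14/182.6 = 7.7% and 21/182.6 = 11.5% of the interval.

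**3. Illustration for return to work (every input assumed)**

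Suppose time to return to work is exponential from injury, with the same median m in both arms and therefore no true difference. The proportion back at work by day t is 1 − 2^(−t/m). Let the shorter-stay arm be called at day 190 (a stay of about 7 days) and the other arm d days later.

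Example with m = 180 and d = 14: 1 − 2^(−190/180) = 0.519 and 1 − 2^(−204/180) = 0.544, a difference of 2.5 points.

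| d (days) | Difference in points over m = 120, 180, 240 days |
|---|---|
| 7 | 1.2 to 1.3 |
| 14 | 2.3 to 2.6 |
| 21 | 3.4 to 3.8 |

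**4. Scale against sampling error**

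The Sample Size section plans 28 per arm. With 51.9% back at work, and if all respond,

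SE of the difference = √(2 × 0.519 × 0.481 / 28) = 0.134, about 13 points.

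The 95% half-width is 1.96 × 13.4 = about 26 points. The illustrated shift is therefore 1.2/13.4 to 3.8/13.4, or roughly 0.1 to 0.3 of a standard error.

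**The case against.** **The intended rule is recoverable.** Discharge is the origin nearly everywhere, and the injury wording is one phrase in a list of data items. This stands. A reader might infer that two rival rules are in use and that patients are being called on different schedules, but nothing in the documents shows that. The phrase still needs correcting.

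**Six months after discharge is a definable time point.** This stands in part. Timing from discharge can be a deliberate choice, but the plan gives no reason for it, and the choice makes the assessment time depend on an outcome under comparison.

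**No difference in stay is documented.** This stands. A reader might infer that DCL patients stay longer, that discharge timing therefore flatters DCL, and that it works against the trial's hypothesis. A longer DCL stay is plausible, since DCL entails intensive care with an open abdomen and a second operation. But the protocol only lists length of stay as an outcome and predicts no difference. The direction would also depend on the outcomes improving with time. The stated hypothesis concerns death or major abdominal complications within 30 days, which this issue does not reach.

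**Return to work does not have two origins.** Correct. The injury phrase covers the health status questionnaires; return to work simply has no origin.

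**The illustration depends on its model.** This stands. If the chance of returning to work starts to run at discharge, which is equally open to assumption, discharge timing gives both arms 182.6 days at risk and creates no difference. And if actual return dates are recorded, an analyst can count from injury and truncate at a common day: a call made on time after discharge always falls at least 182.6 days after injury. The plan does not provide for this. The Data Analysis Plan names the Wilcoxon rank-sum test for continuous outcomes and no method for patients who have not yet returned to work.

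**Conclusion.** The point holds as an inconsistency to be reconciled, together with a modest design weakness. One phrase in Data Collection conflicts with the discharge timing used elsewhere, and time to return to work lacks an origin. Under the discharge rule, a difference in stay of any number of days becomes the same difference in time since injury at the Aim 3 assessment. That step is arithmetic and needs no assumption.

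How large the difference is, and which arm it would favour, cannot be told from the documents. The 1.2 to 3.8 points rest wholly on assumed gaps in stay, assumed medians and a return-to-work hazard running from injury; they are not an estimate of bias in this trial. Even so computed, the shift is small beside the sampling error of a 56-patient trial. Only secondary, patient-centred outcomes are concerned. The change is worth making because it is nearly free.

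**What to change.** State one origin in every place that times the assessment: the title-page subject duration, Secondary outcomes, Time Period, Outcomes, both paragraphs of Data Collection, and Data Handling. Correcting only the outcome sections would leave a new contradiction.

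- Time the Standard Gamble, EQ-5D-5L and PCL-C at six months after randomization, which is in effect the day of injury, with a fixed call window.
- Record the date of return to work, measure the time from randomization, and censor or truncate all patients at a common day. Name the analysis for patients not yet back at work.
- Treat the at-discharge questionnaire as descriptive.
- While editing, settle whether the PCL-C is given at discharge: Secondary outcomes lists it at both times, whereas Outcomes mentions it only at six months.

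The cost is wording and the date used to schedule the call. The six-month assessment is already a single phone contact, and the randomization date is known for every patient. The drawback is that a patient with a very long stay may still be in hospital at the call, so the plan should say how that patient is assessed.

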experienced, Level 1 trauma centers.^{5,6,7} With more patients undergoing DCL, the associated risks and benefits became better understood.⁸ Potential benefits include decreased mortality and avoidance of hypothermia, acidosis, and coagulopathy (the “lethal triad” in trauma surgery). Risks include high rates of incisional hernia, all forms of surgical site infections (SSI), enterocutaneous fistulas, pneumonia, sepsis, and organ failure.^{9,10,11,12} The use of DCL has significant implications not just on mortality, but also on morbidity, patient-centered long-term outcomes, and healthcare resource utilization.

All of the studies comparing injured patients undergoing DEF and DCL are retrospective, subject to survival and collider bias, and have a wide variation in injury severity, transfusion requirements, surgeon rationale, and patient selection. A recent consensus statement in 2015 evaluating the appropriateness of various indications for DCL entirely lacked high-quality evidence. No RCTs assessing DCL exist for trauma.¹³

One difficulty in performing a RCT of DCL is there are a multitude of indications for which a majority of surgeons do not have the clinical equipoise to randomize patients. That is, no surgeon would randomize a patient with a severe liver injury in which the only method of hemorrhage control was gauze packing of the liver – an act which necessitates leaving the abdomen open as the gauze must be removed once bleeding has stopped. If a patient develops such significant bowel edema from resuscitation, the surgeon may not be able to physically close the incision or may do so with such tension that abdominal compartment syndrome (ACS) results.

Given this common operation (at our institution 1 trauma laparotomy is performed every 36 hours), high rate of mortality (26% in all DCLs), high rate of morbidity, and a lack of quality evidence, RCTs to compare DEF and DCL among patients undergoing emergent laparotomy for trauma are needed.

Preliminary Studies

Retrospective cohort study evaluating morbidity following DCL⁵

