For DCL patients, adverse events are the primary outcome. Both patients in the DEF and DCL groups are at risk for the same adverse events and the event rate in the proposed groups is unknown. To assess for harm, blinded, univariate outcomes between the two groups will be assessed every 6 months throughout the study period by a data safety and management board (DSMB), which will be organized by CeTIR and headed by [name]. The DSMB will also include an anesthesiologist, a former trauma patient without a medical background who underwent emergent laparotomy, and an independent statistician. At the first meeting following 50% recruitment, a formal Bayesian analysis will be presented to the DSMB to assess the probability of benefit or harm of DCL.

One potential problem area is surgeon adherence to randomization. While the Division of Acute Care Surgery has an excellent record of trauma surgeon buy in for randomized, controlled trials (Early Whole Blood trial, PROPPR, Irricept®), it remains a concern that surgeons will choose not to enroll potentially eligible patients or fail to implement the randomized treatment. To help mitigate surgeon deviation, preliminary work showing indications for which there is equipoise among practicing surgeons has been performed. Additionally, all emergent laparotomies will be evaluated the following day to assess eligibility. If not randomized, the PI will provide real-time surgeon feedback to improve future compliance. Protocol deviations of randomized patients will be documented and reported in publications. Patients will be analyzed on an intent-to-treat basis, so randomized patients will be statistically analyzed in the group to which they were randomized.

Statistics

Sample Size

Over a 2 year period, we aim to enroll 56 patients, 28 in each arm based upon: 1) preliminary data with a MAC rate of 55% in DCL patients and 18% in the DEF patients, 2) alpha=0.05, 3) power=0.80, and 4) dropout rate=10%.

Approximately 55-66 DCLs are performed per year, therefore over 2 years of patient enrollment, enrolling 56 patients meeting eligibility is realistic.

Table 2: Sample size calculations

Enrolled Patients	Expected Difference in MAC (DCL – DEF)
36	47% (65% – 18%)
56	37% (55% – 18%)
108	27% (45% – 18%)

Randomization

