Allocation will occur through sequentially numbered, opaque envelopes kept in the research assistants' office and opened in the operating room. An independent statistician will determine the randomization sequence and oversee the labeling of cards and envelopes. A 1:1 allocation ratio using a permuted block design of 4 or 6 will be used to ensure equal number of patients in each group.

Randomization will occur during the emergent trauma laparotomy. The research assistant will query the attending trauma surgeon periodically throughout the procedure to determine their equipoise between DCL and DEF. If the patient meets all eligibility criteria, that patient will be randomized to DCL (control) or DEF (intervention). The research staff will open the opaque envelope to notify the attending surgeon which group to which the subject has been randomized.

Data Analysis Plan

The number of screened patients and reasons for exclusion will be reported. Protocol violations and reasons for those violations will be reported and detailed. Differences in primary and secondary outcomes across treatment groups will be compared on an intent-to-treat basis using the Wilcoxon rank-sum test, Pearson's Chi-squared, and Fisher's Exact test, for continuous, binary, and sparse binary outcomes, respectively. Exploratory analyses will model outcomes via linear or logistic regression with treatment as the predictor, controlling for any covariates found to be imbalanced across treatment assignment. An independent statistician will provide all data analyses and present them to the DSMB for review.

Given the small sample size of the trial, we will augment the frequentist model described above with a Bayesian analysis to estimate the probability of treatment effects of DCL and DEF.¹⁷

Ethics

This study qualifies for the "Exception from informed consent required for emergency research" (EFIC) as outlined in the FDA regulation 21CFR50.24.¹⁸

1. Subjects are in a life-threatening situation and collection of valid scientific evidence is necessary to determine the safety and effectiveness of the particular interventions
2. Obtaining informed consent is not feasible because the subject cannot give reasonable consent due to medical condition, intervention must be given before consent can be obtained from a LAR, and cannot prospectively select subject

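### The exploratory regressions choose covariates by observed imbalance, with no threshold, cap or restriction to pre-randomisation variables; one or two prespecified prognostic covariates would serve better

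*Combined protocol and SAP*

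**What the plan says.** Under Statistics, Data Analysis Plan, primary and secondary outcomes are to be "compared on an intent-to-treat basis using the Wilcoxon rank-sum test, Pearson's Chi-squared, and Fisher's Exact test". These comparisons are unadjusted. The plan then adds a second layer: "Exploratory analyses will model outcomes via linear or logistic regression with treatment as the predictor". What else goes into these models is settled by a rule applied to the observed data, namely "controlling for any covariates found to be imbalanced across treatment assignment". It does not say which covariates are candidates, what test or difference counts as imbalance, or how many covariates a model may hold.

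Study Procedures, Data Collection, lists what will be available: "demographics, prehospital and injury information, hospital information including ED, OR and post-operative care, discharge information", among other items. The list runs from before arrival to after surgery, and nothing in the plan limits adjustment to the earlier part.

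On randomisation the plan says "A 1:1 allocation ratio using a permuted block design of 4 or 6 will be used". No stratification factor is stated, so no covariate enters the analysis by design. The planned size is given as "we aim to enroll 56 patients, 28 in each arm".

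**The concern.** In a randomised trial, differences in baseline variables arise by chance. Adjustment helps when a covariate predicts the outcome. An imbalance screen does not look at that, so it can spend scarce degrees of freedom on irrelevant variables and leave out a prognostic one that happens to be balanced.

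Two features of this plan add to that:

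- **Post-randomisation variables are not ruled out.** A damage control patient goes to the ICU with an open abdomen and returns to theatre by definition. Variables describing post-operative care can therefore differ between arms because of treatment. Taken literally, the rule could admit them and adjust away part of the effect.
- **The rule is not reproducible.** With no threshold or candidate list, two competent analysts could fit different models to the same data and both be following the plan.

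At stake is the usefulness of the adjusted estimates. They may be read alongside the unadjusted ones for Aim 4, which seeks effect sizes for planning a multicentre trial.

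**Working it through.** **Inputs from the protocol (Statistics, Sample Size).** Rates 55% and 18%, alpha 0.05 (taken as two-sided), power 0.80, dropout 10%, total 56.

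**1. The plan's own figure.** With the pooled-variance formula,

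n = [1.96·√(2·0.365·0.635) + 0.842·√(0.55·0.45 + 0.18·0.82)]² / 0.37² = 25.4, so 26 per arm.

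Then 26/0.9 = 28.9, so 29 per arm and 58 in total. The arcsine formula gives 25 per arm; 25/0.9 = 27.8, so 28 per arm and 56 in total, as stated. The figure reproduces, and it does not depend on the covariate rule.

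**2. Information available to a model.** Evaluable patients: 28 × 0.9 ≈ 25 per arm. Expected events: 25 × (0.55 + 0.18) ≈ 18, or 28 × 0.73 ≈ 20 with no dropout. That supports very few covariates.

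**3. How often chance triggers the rule.** For k independent balanced covariates screened at level a, the chance that at least one is flagged is 1 − (1 − a)^k.

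- 8 covariates, p<0.05: 1 − 0.95^8 = 34%.
- 10 covariates: 40% at p<0.05, 65% at p<0.10.
- 20 covariates: 64% at p<0.05, 88% at p<0.10.

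**4. Power (simulation).** Several independent runs of 4,000 to 6,000 trials per scenario used 25 per arm, overall rates 55% and 18%, and a linear model for the risk difference with HC2 standard errors. There were eight candidate covariates, one of them prognostic, screened at p<0.05. The number of candidates, the threshold and the prognostic strength are assumptions; the documents give none of them. Ranges show the spread between runs.

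| Log-odds per SD | Unadjusted | One prespecified | Imbalance rule | Prespecified minus rule (points) | Prespecified minus unadjusted (points) |
|---|---|---|---|---|---|
| 0.3 | 0.82 | 0.81 | 0.80 | 1 | −1 |
| 0.5 | 0.82 | 0.81 | 0.79 | 2 | −1 |
| 0.7 | 0.82 | 0.83 | 0.80 | 3 | 1 |
| 1.0 | 0.81–0.82 | 0.84–0.86 | 0.79–0.80 | 4–6 | 2–4 |
| 1.3 | 0.82 | 0.87–0.88 | 0.80 | 7–8 | 5–6 |

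The Monte Carlo standard error of one power figure is about √(0.8·0.2/5000) = 0.006, so a one-point gap in the table is small against simulation noise.

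**5. Precision at log-odds 1.0.** The SD of the risk difference was 0.125–0.126 unadjusted, 0.117–0.119 prespecified and 0.126 under the imbalance rule. Prespecification cuts it by about 6% ((0.125 − 0.117)/0.125); the rule does not reduce it.

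**6. Logistic version.** With 15 candidates, two of them prognostic, and log-odds 0.5 / 1.0 / 1.5:

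- unadjusted: 0.79 / 0.81 / 0.80
- both prognostic covariates prespecified: 0.81 / 0.88 / 0.91
- imbalance at p<0.05: 0.75 / 0.78 / 0.77
- imbalance at p<0.10: 0.74 / 0.76 / 0.77

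The ordering of prespecified over rule is the same, with a wider gap of 6 to 14 points.

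**7. Type I error.** In the linear runs it was 0.048–0.056 for all three methods. In the logistic runs a fixed imbalance threshold gave 0.035–0.047. It rose to 0.067–0.082 only when the best result was taken from the unadjusted model and the p<0.05, p<0.10 and p<0.20 selections.

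**The case against.** The strongest reply is that little depends on these models. They are labelled exploratory, the main comparisons are unadjusted and by intention to treat, and the stated answer to the small sample is a Bayesian analysis rather than covariate adjustment. All of that stands, and it keeps the point modest.

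The gain from prespecification also depends on assumptions. At log-odds 0.5 or below, one prespecified covariate did not beat the unadjusted linear analysis. With all eight candidates moderately prognostic (0.5 each), the rule matched a single prespecified covariate on power (0.81 each; 0.82 unadjusted) and had a slightly smaller SD (0.1225 against 0.124). That stands too: the rule is not worse in every setting.

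A reader might infer more than the documents support:

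- **That the trial's error rate is inflated.** The primary test does not use the rule, and a fixed threshold does not inflate type I error. Inflation needs a choice of the best result across thresholds, which the plan does not propose; it assigns all analyses to an independent statistician.
- **That post-operative variables will be adjusted for.** The plan does not say so. It only fails to exclude them.
- **That the protocol identifies the main prognostic factors in its own patients.** The Background sentence saying that studies "have a wide variation in injury severity, transfusion requirements, surgeon rationale, and patient selection" is about earlier retrospective comparisons. This trial's exclusions, such as ongoing transfusion and persistent hypotension, may narrow that variation.
- **That red-cell units given before randomisation are already recorded.** Randomisation takes place during the laparotomy, and no section says that transfusion is recorded up to that moment.

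**Conclusion.** The concern holds for the exploratory models only. Selecting by imbalance, with threshold, number and timing all open, is a weaker rule than naming one or two prognostic pre-randomisation covariates. With one prognostic covariate among eight candidates, its power and precision are about the same as, or slightly below, those of no adjustment. It loses roughly 1 to 8 power points against the prespecified covariate over log-odds 0.3 to 1.3 per SD with 25 evaluable patients per arm. The lower end of that range is close to simulation noise. A gain over the unadjusted analysis should be expected only if the covariate is at least moderately prognostic, about 0.7 or more.

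The sample size, the unadjusted primary test and its type I error are unaffected. The case for change is that the better rule is cheap, reproducible and closes the route to adjusting for consequences of treatment. It does not rest on any main conclusion being at risk.

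**What to change.** Replace the covariate phrase in the Data Analysis Plan with wording such as: *Exploratory adjusted models will include one or two prognostic covariates measured before randomisation and named before outcomes are seen by arm (for example injury mechanism and an injury severity measure, as available in the case report form or trauma registry), whether or not they are balanced; for the primary outcome an adjusted risk difference with 95% CI will be reported.*

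Keep the unadjusted test primary. If an imbalance-driven model is still wanted, label it a sensitivity analysis, limit it to pre-randomisation variables and state its threshold. Because outcomes by group go to the DSMB every 6 months, the covariates should be fixed before the first such report, or by someone who has not seen one.

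The cost is one sentence and a check that the chosen variables are recorded as they stood before randomisation. The trade-off is commitment in advance, with a loss of about one power point in the exploratory model if the covariates turn out to be weakly prognostic.
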